## STUDY SYNOPSIS

EudraCT Number: 2015-002117-30 Protocol Number: 000010/BT Protocol Code: JTA-KOA1	Test product: JTA-004 Reference: Synvisc-One®
Sponsor: Bone Therapeutics S.A., [name]	
Title: A two-stage 6-month, Multicentre, Randomised, Double-blind, Controlled Study on the Safety and Efficacy of Single Intra-articular Administration of JTA-004 in Patients with Symptomatic Knee Osteoarthritis	
Phase of Development: Two-stage Phase II/Phase III trial	
Number of Centres / Countries: up to 15 centres in Belgium	
Planned Study Period: Total recruitment period: until 164 patients have been included (this number may be adjusted upon sample size reassessment at interim analysis). Total study follow-up period: 6 months	
Study design: This study is a seamless two-stage prospective, randomized, double-blind controlled Phase II/Phase III trial including 3 JTA-004 strengths with 1 reference product. The initial phase of the two-stage design plans for selection of the best JTA-004 strengths for a confirmatory phase testing for superiority compared to a best in class reference treatment.	
Planned Number of Patients: A total of 164 patients are planned.	
Medical Condition under Investigation: symptomatic osteoarthritis of the knee with Kellgren-Lawrence grade II and III.	

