**JTA- KOA1 - Clinical Study Protocol**

JTA-KOA1-CSP

V 04

Author: EB

Date: May 10, 2017

Pg. 8/114

*Primary Endpoint*

The primary endpoint is the change between baseline and Month 6 of the Western Ontario and McMaster Universities (WOMAC® VA3.1 pain subscale (subscale A).

Primary study objectives are (i) the selection of the best JTA-004 strength and (ii) superiority assessment of the best JTA-004 strength efficacy to the reference or (iii) stop the trial at interim analysis for futility. They will be determined as follow:

- For selection of best JTA-004 strength, by comparing the different JTA-004 strengths to the reference with respect to the WOMAC® VA3.1 pain subscale score (mean differences between baseline and Month 3)
- For superiority assessment, by comparing the best JTA-004 strength and reference on the mean differences in WOMAC® VA3.1 pain subscale score between baseline and Month 6, assuming a mean between group difference of 7 mm in favor of the best JTA-004 strength (i.e., difference JTA-004 minus Reference of -7 mm) with a standard deviation of 10 mm.

The following hypothesis is stated to show superiority of JTA-004 to Reference:

- H0: The difference in the mean change from baseline at Month 6 between JTA-004 and Reference is superior or equal to 0.
- H1: The difference in the mean change from baseline at Month 6 between JTA-004 and Reference is inferior to 0.

The secondary efficacy endpoints are:

- WOMAC® VA3.1 pain subscale (WOMAC® subscale A) at Month 3
- WOMAC® VA3.1 total score over the time

*Safety Analysis*

All safety analyses will be conducted on the safety population and tabulated by treatment group.

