### 3 INVESTIGATIONAL PLAN

#### 3.1 General Study Design

The present study is a two-stage, prospective, multicentre, randomised, double-blind, controlled study comparing the safety and efficacy of JTA-004 single IA administration in patients with symptomatic knee OA to a reference HA preparation having shown superiority to placebo.

The main objectives of the study is to select the best among 3 different JTA strengths and demonstrate its superiority to a reference treatment with respect to knee pain at Month 6.

After signing the Informed Consent Form (ICF), patients, if eligible (according to the eligibility criteria, cf. Section 3.5), will be randomised on a 1:1:1:1 ratio into the JTA-004 or the reference groups. Treated patients will be followed up during 6 months with post-treatment assessments performed at 2 weeks, 3 months and 6 months.

Experimental design	Prospective, multicentre, double-blind, reference-controlled study
Number of centres	up to 15
Countries	Belgium
Number of Patients	116 patients (incl. 10% drop-out) for the interim analysis where sample size will be re-estimated based on first 3 months of follow-up data. 164 patients (incl. 10% drop-out) for the whole study.
Duration of Study	6 months of follow-up
Osteoarthritis Site	Knee
Osteoarthritis Type	Kellgren-Lawrence grade II and III
Treatment	JTA-004 50 (2 ml), JTA-004 50 (4 ml) & JTA-004 100 (2 ml) Reference (6 ml)
Procedures	JTA-004 and reference single IA administration performed ambulatory
Patient Allocation	1:1:1:1 randomisation schedule
Study Time Points	2 weeks, 3 months and 6 months after administration

Self-contained study

Data collection: Case Report Form (eCRF)

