**10 STATISTICAL CONSIDERATIONS AND METHODS OF ANALYSIS****10.1 Analysis Populations**

Four treatment groups including the reference and JTA-004 groups will be studied and compared. Comparisons with respect to reference will be performed in a superiority design.

Patient populations are defined as followed:

- The safety set (SAF) will include all treated patients.
- The Full Analysis Set (FAS) will include all randomised and treated patients.
- The Per-Protocol (PP) set will include all patients of the FAS without any major protocol deviation.

Demographics, baseline characteristics and efficacy variables will be analysed using the FAS. These analyses will be performed as randomised and treated.

The FAS will be considered as primary cohort for the selection of the best JTA-004 product and for the superiority analysis. Primary criterion and corresponding variables will be analysed in the FAS and in the PP.

All safety variables will be analysed on an as-treated basis using the SAF.

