### 10.9 Sample Size Estimation

The sample size calculation for the superiority trial for the primary endpoint – change in WOMAC® VA3.1 pain subscale from baseline to Month 6 - is based the following assumptions:

- The mean pain difference of patients treated with the JTA-004 and those treated with the reference treatment is assumed to be -7 mm (i.e. the mean JTA-004 treatment is 7 mm better than the reference). The absolute mean difference is set to 7 mm which is below the accepted MCID of the WOMAC® VA3.1 pain subscale, which is 10 mm (Ehrich *et al.*, 2000; Bellamy *et al.*, 2001);
- The standard deviation of the mean pain difference between the two treatments, estimated from the Borrás-Verdera *et al.*, 2012 and Pavelka and Uebelhart., 2011 data, are in the range of 4.7 to 6.6 mm for sample sizes between 48 and 24, respectively. To ensure maximal power, a standard deviation value of 10.5 was used for sample size estimation.);

Under the scenario of a mean between group difference of -7 mm (i.e., JTA-004 is better than control by a mean of 7 mm) with a standard deviation of 10.5 mm, thirty-seven (37) patients per group are required for analysis, reaching a power of 80% to test for superiority, keeping the type I error at 0.05 (two-sided). This would allow collecting enough efficacy data per group while avoiding exposing too many patients.

The level of drop-out is estimated to 10%. Thus 41 patients per group have to be included.

As recruitment will continue in all 4 treatment groups until the final analysis, the maximum total number of included patients will be 164 (4 x 41).

JTA-KOA1 - Clinical Study Protocol

JTA-KOA1-CSP	V 04	Author: EB	Date: May 10, 2017	Pg. 84/114
--------------	------	------------	--------------------	------------

[REDACTED]

[REDACTED]

[REDACTED]

[REDACTED]

[REDACTED]

[REDACTED]

[REDACTED]

[REDACTED]

[REDACTED]

[REDACTED]

[REDACTED]

[REDACTED]

[REDACTED]

[REDACTED]

[REDACTED]

[REDACTED]

[REDACTED]

[REDACTED]

[REDACTED]

[REDACTED]

[REDACTED]

[REDACTED]

[REDACTED]

[REDACTED]

[REDACTED]

[REDACTED]

[REDACTED]

[REDACTED]

[REDACTED]

[REDACTED]

JTA-KOA1 - Clinical Study Protocol

JTA-KOA1-CSP	V 04	Author: EB	Date: May 10, 2017	Pg. 85/114
--------------	------	------------	--------------------	------------

[REDACTED]

[REDACTED]

[REDACTED]

[REDACTED]

[REDACTED]

[REDACTED]

[REDACTED]

[REDACTED]

[REDACTED]

[REDACTED]

[REDACTED]

[REDACTED]

[REDACTED]

[REDACTED]

[REDACTED]

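### The 37 per group and 80% power in Section 10.9 belong to one unadjusted comparison, not to a test that protects alpha after the best of three strengths is selected

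*Combined protocol and SAP*

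**What the plan says.** Section 10.9 assumes a difference of 7 mm and an SD of 10.5 mm and arrives at 37 evaluable patients per group, "reaching a power of 80% to test for superiority, keeping the type I error at 0.05 (two-sided"). With 10% drop-out this becomes 41 per group, and "the maximum total number of included patients will be 164 (4 x 41"). All four arms recruit to the end.

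The synopsis describes "selection of the best JTA-004 strengths for a confirmatory phase testing for superiority". The first step is set out as "For selection of best JTA-004 strength, by comparing the different JTA-004 strengths to the reference", on the change from baseline to Month 3. The second compares the best strength with reference on the change to Month 6, and here the synopsis gives an SD of 10 mm. A third possible outcome is to "stop the trial at interim analysis for futility". Under Section 10.1, "The FAS will be considered as primary cohort for the selection of the best JTA-004 product and for the superiority analysis".

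Section 3.1 plans "116 patients (incl. 10% drop-out) for the interim analysis where sample size will be re-estimated based on first 3 months of follow-up data". The synopsis says of the 164 that "this number may be adjusted upon sample size reassessment at interim analysis".

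The table of contents lists Section 10.11 on multiplicity and a Section 10.12 whose title is blacked out. The text of neither is visible. The reference list includes a methods paper on adaptive Dunnett testing with treatment selection and one on Hochberg's procedure.

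**The concern.** The visible sample size calculation mentions neither three strengths nor selection. If the confirmatory test pays for selection with a stricter critical value, the power at 37 per group is not the power of a single comparison at the ordinary 5% level. A reader of Section 10.9 would take the chance of missing a 7 mm effect to be 20%. With one effective strength and a Dunnett-type test, it is nearer 31%.

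Section 10.9 states one effect and does not say what is assumed for the other two strengths, so the reader cannot tell which power applies. Re-estimation might recover lost power, but only if the total may exceed 164, and the visible text does not settle that.

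**Working it through.** **Inputs from the documents.** Difference 7 mm, SD 10.5 mm, two-sided 0.05 and 37 per group (Section 10.9); SD 10 mm (synopsis); three strengths plus reference, 1:1:1:1; interim at 116 patients (Section 3.1), so 116/4 = 29 per arm and 29 x 0.9 = about 26 evaluable.

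**Assumptions not in the documents.** The strength with the best Month 3 mean is selected, on efficacy only; one strength goes forward; Month 3 effects equal Month 6 effects; Month 3-Month 6 correlation is 0.3 to 1.0; no futility stop; no re-estimation.

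**1. The plan's own figure.** For a two-sample t-test the noncentrality is 7 / (SD x √(2/n)).
- n = 36: 7 / (10.5 x √(2/36)) = 2.828; critical t (70 df) = 1.994; power 79.7%.
- n = 37: 7 / (10.5 x √(2/37)) = 2.867; critical t (72 df) = 1.993; power 80.8%.

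So 37 is the correct size for one unadjusted comparison.

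**2. Same size, Dunnett critical value.** For three comparisons with a shared control, one-sided 0.025 and 4 x 37 - 4 = 144 df, the critical t is 2.374.
- SD 10.5: noncentrality 2.867, power 68.9%.
- SD 10: noncentrality 7 / (10 x √(2/37)) = 3.011, power 73.7%.

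**3. Adding selection at the interim.** Simulation: select on Month 3 in 26 per arm, test at Month 6 in 37 per arm. Success means that the selected strength is truly better than reference and is declared superior. SD is 10.5.

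| True effects (mm) | Single-step Dunnett | Step-down Dunnett |
|---|---|---|
| 7 / 0 / 0 | 68-69% | 68-69% |
| 7 / 3.5 / 3.5 | 62-70% | 63-70% |
| 7 / 7 / 0 | 72-82% | 75-82% |
| 7 / 7 / 7 | 74-87% | 80-87% |

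An adaptive (conditional-error) Dunnett test gives 69-70% with one working strength and 81-89% with three equal strengths over the same correlations. Hochberg gives 66-67% and 80-88%. With one working strength, the right strength is selected in about 98.5% of runs, so the loss comes from the critical value and hardly depends on the correlation.

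**4. Keeping the unadjusted cutoff instead.** If all three strengths equal reference, the selected strength is declared superior in 3.4% (correlation 0.3) to 5.7% (correlation 1.0) of trials, against 2.5% intended. With one working strength, therefore, 37 per group, 80% power and a protected two-sided 0.05 do not hold together under a Dunnett-type test.

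**5. Why the status of 164 matters.** With one working strength, SD 10.5 and Dunnett, 80% power needs 47-48 evaluable per group. By the protocol's drop-out method, 47 x 1.10 = 51.7, so 52, and 48 x 1.10 = 52.8, so 53. Four arms then give 208-212, above 164. This shows only what a cap would prevent; it is not a proposed size.

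**The case against.** A reader might infer that the plan has no multiplicity control, or that 37 is an arithmetic mistake. The documents support neither. The sum is right for the test it describes, and a multiplicity section is listed whose text cannot be seen. That text may specify the test, the selection rule and an adjusted power figure, so its absence here is not a gap in the plan.

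A reader might also infer that the trial is underpowered. That goes too far, for four reasons:
- **Scenario.** No passage says that two strengths are inert. They are strengths of one product, and with two or three about equally effective, power can reach or exceed 80%.
- **Test version.** The 74% low end with three equal strengths comes from a fixed single-step cutoff, which nothing visible specifies. The adaptive version, closer to the cited methods paper, stays above 80% in that scenario at correlations of 0.3 or more (78% at zero).
- **Variance.** The one-strength figure rises from 69% to 74% at the synopsis SD. Adjusting for baseline could raise it further. Section 10.7.6 names ANCOVA for the secondary endpoints, while the visible text of Section 10.7.5 names no model. An assumed baseline correlation of 0.3-0.5 would give about 74-82%.
- **Re-estimation.** It is planned and could raise the final size, so a fixed 37 is not the trial's full operating characteristic.

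All four stand as limits on the size. They do not alter the fact that the 80% in Section 10.9 is a pairwise figure, nor that the visible text leaves the effects of the other strengths unstated. In the other direction, a futility stop could only lower power.

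**Conclusion.** The point holds as a conditional one. The 80% in Section 10.9 is the power of a single unadjusted comparison. If the selected strength is tested with a Dunnett-type adjustment, power at a fixed 37 per group is about 69% with one working strength, roughly 11 points below the stated figure, and about 74% if the SD is 10 mm. With three equally effective strengths it is roughly 74-89% and there may be no shortfall. These figures rest on the selection rule, Month 3 effects and correlation listed as assumptions above, and on no futility stop and no re-estimation. They do not show that alpha is unprotected or that an adjusted power calculation was never made.

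The conflict over 164 is separate and visible on the page: Section 10.9 calls it a maximum, while the synopsis and Section 3.1 provide for re-estimation.

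**What to change.** In Section 10.9:
- Label the 80% as the power of one pairwise comparison.
- State the power of the selection-adjusted test actually used, or carry it over if the text that is not visible already gives it.
- List the effects assumed for the other strengths at Months 3 and 6, the Month 3-Month 6 correlation and the selection rule, and say whether futility stopping and re-estimation are included.
- Use one SD, 10 or 10.5 mm, here and in the synopsis.

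Separately, reconcile Section 10.9 with the synopsis and Section 3.1 by saying whether 164 is a cap on re-estimation or a starting number.

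The cost is a short recalculation and a few sentences, with a possibly less favourable stated power. No additional patients are requested.

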**10.13 Independent Data Monitoring Committee**

*10.13.1 Members*

The IDMC will consist of 2 persons who are not involved in any kind in the study. One person will be a statistician and one person will be a Rheumatologist.

*10.13.2 Responsibilities*

The members of the IDMC are responsible for the data analysis and medical interpretation concerning clinical relevance and toxicity of the interim analysis. They will summarize the results and give a written report to the sponsor.

*10.13.3 Study Data to be sent to the IDMC*

[REDACTED]

- [REDACTED]
- [REDACTED]
- [REDACTED]
- [REDACTED]

**JTA-KOA1 - Clinical Study Protocol**

JTA-KOA1-CSP

V 04

Author: EB

Date: May 10, 2017

Pg. 86/114

■ [REDACTED]

[REDACTED]

*10.13.4 Unblinding Procedure*

To ensure the overall blinding of the study, the treatment of patients included in the interim analysis will be unblinded by the Independent Data Monitoring Committee (IDMC, see 7.5.1).

The statistician of the IDMC will receive the sealed envelope containing the complete randomization list. Arrival has to be confirmed in writing (confirmation by e-mail will be acceptable). He will extract the medication numbers included in the interim analysis and perform the statistical analysis as described above.

The IDMC will not disclose any information regarding the contents of the randomization list to the sponsor.

*10.13.5 Results*

The results of the interim analysis will be sent to the Sponsor.

**JTA-KOA1 - Clinical Study Protocol**

JTA-KOA1-CSP

V 04

Author: EB

Date: May 10, 2017

Pg. 87/114

**11 STUDY MANAGEMENT****11.1 Source Documents/Data**

Each Investigation Site will maintain and archive all appropriate medical and research records related to the trial, in compliance with ICH E6 GCP Section 4.9, and regulatory and institutional requirements for the protection of patient confidentiality.

Source data are all information, certified copies of original records of clinical findings, observations, or other activities in a clinical trial necessary for the reconstruction and evaluation of the trial.

Source documents are printed, optical or electronic document containing source data. They may include, but are not limited to, patient's medical records, hospital charts if any, clinical and office charts if any, the Investigator's patient study files, pharmacy dispensing records, recorded data from automated instruments, as well as the results of diagnostic tests, such as radiographs, laboratory and urine pregnancy tests when applicable.

The following information should be entered into the patient's medical records:

- Patient name, surname and date of birth
- Patient's contact information
- Medical chart (e.g., hospital source document tracking number), if any
- A statement that ICF was obtained with the date of ICF collection and a documentation on the person who conducted the Informed Consent Process
- Dates of initial screening and all patient visits
- The patient identification number
- The study title and/or the protocol number and the name of the Sponsor
- Medical/surgical relevant history and physical examination
- Results of blood pressure, heart rate, respiratory rate and body temperature
- Results of urine pregnancy test (only for female with childbearing potential)
- Results of radiographs when applicable

JTA-KOAI - Clinical Study Protocol				
JTA-KOAI-CSP	V 04	Author: EB	Date: May 10, 2017	Pg. 88/114

- Laboratory results notes/reports
- All concomitant medications and concurrent procedures
- Occurrence and status of any AE and SAE
- The date the patient exited the study, with a note as to whether the patient completed the study or the reason for discontinuation

The questionnaires are to be completed directly by the patient. The original pages, considered as source data, will be kept and filed on site (in the ISF).

All data captured for this study are to be recorded in the patient's notes first and then entered in the eCRF.

## 11.2 Monitoring

Before study initiation, the CRA will visit the Investigating Sites to evaluate the feasibility of participating to the study (e.g., patient recruitment, staff availability, facilities, equipment). During the Study Initiation Visit, the CRA will initiate the Principal Investigator and the site staff in order to train the PI and the site staff on the Study Protocol and trial-related procedures, and verify good understanding of GCP (e.g., Investigator's responsibilities) and any other applicable Community and national legal and regulatory requirements, notably as regards standards of quality and safety for the procurement (including patient selection and inclusion), testing, distribution, administration, and traceability of human tissues and cells, as well as notification and reporting of any SAE and/or Serious Adverse Safety/Quality Events.

Very shortly after the first patient inclusion, an on-site monitoring visit will take place in order to verify the adherence to the protocol and study procedures, and thus avoiding any non-compliance in the future inclusions, if applicable.

During the course of the study, on-site monitoring visits and regular contacts with the Investigation Sites will be conducted by the Monitor in order to provide detailed information and support the Investigator(s), and to assess that the study is performed in compliance and accordance to the protocol, ICH-GCP, and all applicable regional and national regulatory requirements (see the reference documents in Section 12).

**JTA-KOA1 - Clinical Study Protocol**

JTA-KOA1-CSP

V 04

Author: EB

Date: May 10, 2017

Pg. 89/114

For instance, the following aspects will be closely verified:

- Procurement of signed and dated ICF
- Patient rights, including protection of privacy and confidentiality of personal data and medical records, wellbeing, and safety
- Patient recruitment, eligibility, selection, and inclusion
- Study procedures, including laboratory tests, investigation-related procedures and imaging procedures, if any
- Investigational medicinal product receipt, verification, and final delivery by the Pharmacist
- Investigational medicinal product receipt and verification by the Investigator
- Investigational medicinal product accountability and traceability
- SAE notification and reporting
- Emergency and pregnancy procedures
- Data generation and collection processes
- Accuracy of data collected and recorded in the eCRF
- Facilities and Site staff
- ISF (and other on-site source documentation)

Any detected non-compliance with the protocol, GCP or any other applicable Community and national legal and regulatory requirements will be fully documented by the Monitor with the explanation provided by the Investigator on a deviation log and a Note to File, when applicable. This log will include the patient identification number, the date of deviation occurred and a summary of the deviation. All protocol deviations that have occurred during the study should be classified as minor or major. A patient with a major deviation is not included in the PP.

During the monitoring visits, the Investigator and clinical study staff should be available for questions, verification of data from the source documentation, and possible corrections to the eCRF.

**JTA-KOA1 - Clinical Study Protocol**

JTA-KOA1-CSP	V 04	Author: EB	Date: May 10, 2017	Pg. 90/114
--------------	------	------------	--------------------	------------

Following each monitoring visit, a follow-up letter will be sent to the Investigator detailing any action required by either the site staff or the Monitor. Any action must, wherever possible, be addressed immediately or by the next scheduled monitoring visit.

The Monitor will continuously be reachable and available between visits if the Investigator(s), or other study staff at the site, needs additional information and/or advice.

The study site may also be patient to quality assurance audit by the Sponsor as well as inspection by appropriate Regulatory Agencies.

Investigators shall provide a curriculum vitae or equivalent. The curriculum vitae shall give name, date/place of birth, address, and place of work, and shall show the training, appointments, and any other information that will confirm the suitability of the clinical Investigator to be responsible for the clinical trial. All Investigators or other responsible people should be listed together on the "Site Signature and Delegation log". This log, kept up to date in the Investigator Site File, will record examples of each individual's handwriting, signature/initials and job title as well as the tasks the Investigator has delegated to his staff (with date of delegation). The Investigator must sign this log to indicate his/her authorisation.

